15.21 Background

Pembrolizumab is a potent humanized IgG4 monoclonal antibody with high specificity of binding to the PD-1 receptor, thus inhibiting its interaction with PD-L1 and PD-L2. Based on preclinical *in vitro* data, pembrolizumab has high affinity and potent receptor blocking activity for PD-1.

15.22 Formulation

Pembrolizumab is available as a liquid 25 mg/mL, 100 mg/vial.

15.23 Preparation and storage

Vials should be stored in the refrigerator at temperatures between 2-8°C.

Drug concentrate is further diluted with normal saline (or 5% dextrose in the concentration range of 1 to 10 mg/mL) in IV containers made of polyvinyl chloride (PVC) or non-PVC material. The infusion solution in the IV bag should be immediately administered. Diluted pembrolizumab solutions may be stored at room temperature for a cumulative period of up to 4 hours. This includes room temperature storage of admixture solutions in the IV bags and the duration of infusion. In addition, IV bags may be stored at 2-8°C for up to a cumulative time of 20 hours. This 24-hour total hold time from dilution may include up to 6 hours at room temperature

15.24 Administration

Pembrolizumab is administered by intravenous infusion over 30 minutes via a 0.22 micron in-line filter. The final infusion volume must be between 1 and 10 mg/mL. Maximum rate of infusion should not exceed 6.7 mL/minute through a peripheral or indwelling catheter. Flush the line with 0.9% NaCL following the completion of the infusion.

15.25 Pharmacokinetic information

- a) Absorption – Because pembrolizumab is administered intravenously, it is immediately and completely bioavailable. Steady-state concentrations of pembrolizumab are reached by 16 weeks of repeated dosing with a Q3W regimen, and the systemic accumulation is 2.1-fold. The peak concentration, trough concentration, and area under the plasma concentration versus time curve at steady state of pembrolizumab increased dose proportionally in the dose range of 2 to 10 mg/kg Q3W.
- b) Distribution – Pembrolizumab has a limited volume of distribution.
- c) Excretion – CL is approximately 23% lower after achieving maximal change at steady state compared with the first dose. The terminal elimination half-life ($t_{1/2}$) is estimated to be 22 days at steady state.
- d) Metabolism - Pembrolizumab is catabolized through non-specific pathways; metabolism does not contribute to its CL.

15.26 **Potential Drug Interactions:** There are no known significant drug interactions.

15.27 Known potential adverse events:

Very common known potential adverse events, $\geq 10\%$:

Skin and subcutaneous tissue disorders: Pruritus, skin rash
Gastrointestinal disorders: Diarrhea, nausea, abdominal pain
General disorders and administration site conditions: fatigue

Common known potential adverse events, $>10\%$:

Blood and lymphatic system disorders: anemia
Immune system disorders: infusion related reaction
Endocrine disorders: hyperthyroidism, hypothyroidism
Metabolism and nutrition disorders: decreased appetite
Nervous system disorders: headache, dizziness, dysgeusia
Respiratory, thoracic, and mediastinal disorders: pneumonitis, dyspnea, cough
Gastrointestinal disorders: colitis, vomiting, constipation, dry mouth
Skin and subcutaneous tissue disorders: severe skin reactions, vitiligo, dry skin, erythema
Musculoskeletal and connective tissue disorders: arthralgia, myositis, musculoskeletal pain, arthritis, pain in extremity
General disorders and administration site conditions: asthenia, edema, pyrexia, influenza like illness, chills
Investigations: alanine aminotransferase increased, aspartate aminotransferase increased, blood alkaline phosphatase increased, blood creatinine increased

Uncommon known potential adverse events, 1% - 10%:

Infusion related reactions

Blood and lymphatic system disorders: neutropenia, thrombocytopenia, leukopenia, lymphopenia, eosinophilia
Endocrine disorders: hypophysitis, adrenal insufficiency, thyroiditis, hypopituitarism
Metabolism and nutrition disorders: type I diabetes mellitus, hyponatremia, hypokalemia, hypocalcemia
Psychiatric disorders: insomnia, confusional state
Nervous system disorders: epilepsy, lethargy, peripheral neuropathy
Eye disorders: uveitis, dry eye
Cardiac disorders: myocarditis, atrial fibrillation
Vascular disorders: hypertension
Gastrointestinal disorders: pancreatitis
Hepatobiliary disorders: hepatitis
Skin and subcutaneous tissue disorders: lichenoid keratosis, psoriasis, alopecia, dermatitis, dermatitis acneiform, eczema, hair color changes, papule
Musculoskeletal and connective tissue disorders: tenosynovitis
Renal and urinary disorders: nephritis, acute kidney injury
Investigations: blood bilirubin increased, amylase increased, hypercalcemia

Rare known potential adverse events, $<1\%$ (Limited to important or life-threatening):

Blood and lymphatic system disorders: immune thrombocytopenic purpura, hemolytic anemia
Immune system disorders: sarcoidosis
Nervous system disorders: Guillain-Barre syndrome, myasthenic syndrome
Gastrointestinal disorders: small intestinal perforation

Skin and subcutaneous tissue disorders: toxic epidermal necrolysis, Stevens-Johnson syndrome, erythema nodosum

The risk profile for pembrolizumab also includes two important potential risks: a) myasthenic syndrome, and b) an increased risk of severe complications (such as early severe graft versus host disease and veno-occlusive disease) of allogeneic transplant in patients with hematologic malignancies who have previously been treated with PD-1 inhibitors.

15.28 Drug procurement
Commercial supply.

15.29 Nursing Guidelines

15.291 Pembrolizumab side effects vary greatly from those of traditional chemotherapy and can vary in severity from mild to life threatening. Instruct patients to report any side effects to the study team immediately. Side effects may be immediate or delayed up to months after discontinuation of therapy. Most side effects are reversible with prompt intervention of corticosteroids.

15.292 Diarrhea can be seen, however is less common than that seen with anti-CTLA-4 agents. However it can be severe, leading to colonic perforation. Instruct patients to report ANY increase in the number of stools and/or change in baseline, blood in the stool, abdominal pain to the study team immediately.

15.293 Rash/pruritis/dermatitis is seen. Patients should report any rash to the study team. Treat per Section 9.0 and monitor for effectiveness.

15.294 Monitor LFTs closely as elevations in these levels could indicate early onset autoimmune hepatitis. Patients should also be instructed to report any jaundice, or right upper quadrant pain to the study team immediately.

15.295 Pneumonitis can be seen and may be mild (only seen on imaging) to severe. Patients should be instructed to report any SOB, dyspnea, cough, chest pain, etc. to the study team immediately. Patients reporting these symptoms should have a pulse ox checked and consider immediate imaging per the treating MD.

15.296 Endocrinopathies (including hypopituitarism, hypothyroidism, hypophysitis, and adrenal insufficiency) are seen with this agent. Patients may present only with the vague sense of fatigue and “not feeling well.” Additional symptoms may be that of nausea, sweating and decreased activity tolerance. Instruct patients to report these signs or symptoms immediately and obtain appropriate labs as ordered by MD.

15.297 Patients who are started on steroid therapy for any side effects of pembrolizumab toxicity should be instructed to take the steroids as ordered, and not to discontinue abruptly as symptoms may return and be severe. Patients may be on steroid therapy for weeks. Instruct patients to report any increase or change in side effects with any dosage decrease as patients may need a slower taper.

15.298 Fatigue is common and may or may not be associated with immune related side effects. Assess patient’s fatigue level prior to each cycle of therapy and report any changes to the study team.

- 15.299a Patients should avoid receiving live vaccines within 30 days of study drug administration or per other study guidelines.
- 15.299b Patients who have undergone an allogenic bone marrow transplant, have an increased risk of severe complications including early GVHD, and veno-occlusive disease, if they have previously been treated with pembrolizumab
- 15.299c Myocarditis has been reported and associated with pembrolizumab. Instruct patients to report chest pain, SOB, or dyspnea to study team immediately and/or seek emergency medical attention.
- 15.299d Autoimmune hematologic disorders including ITP and hemolytic anemia have been reported. Monitor blood counts closely and report any abnormalities to the study team.
- 15.299e Rare neurologic disorders including Guillain-Barre syndrome and myasthenia gravis have been reported. Instruct patients to report any neurologic symptoms including weakness, paresthesias or numbness, tingling to the study team immediately.

16.0 Statistical Considerations and Methodology

16.1 Primary Endpoint

The primary endpoint is progression-free survival (PFS) at 6 months (PFS6) after registration. Six months is defined as 27 weeks.

16.2 Secondary Endpoints

Secondary endpoints include: overall response rate (ORR), overall survival (OS), incidence of adverse events, and quality of life.

16.3 Sample Size

We plan to accrue 22 evaluable patients. Evaluable patient is defined as those who are eligible, consented, are positive for FGF19, received any protocol treatment, and are without major violation. With 22 evaluable patients, we have 80% power to detect PFS6 from 25% (historical control) to 47%, assuming a 1-sided significance level of 0.1 and an accrual rate of 2 patients per month.

The trial has a single interim analysis for futility and the overall type I error rate is controlled. The interim analysis will be considered non-binding. The accrual will not be halted for the interim analysis.

We anticipate accruing an additional 3 patients to account for ineligibility, cancellation, major treatment violation, or other reasons. Therefore, maximum accrual is projected to be 25 patients. Sample size calculation was based on simulation using R.

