16.4 Statistical Analysis

Interim analysis will be conducted around 6 months after the 11th evaluable patient has been enrolled and the data from the third re-staging scan, if available, has been entered into the electronic database. The PFS6 rate will be calculated using the Kaplan-Meir method. The study may temporarily close to accrual if the PFS6 rate is $\leq 30\%$ at the interim analysis.

Final analysis will be conducted around 6 months after the 22nd evaluable patient has been enrolled and the data from the third re-staging scan, if available, has been entered into the electronic database. The PFS6 rate will be calculated using the Kaplan-Meir method and 80% confidence interval will be calculated using Greenwood's formula with logit transformation. The combination therapy will be declared as promising for future study if the lower bound of the 80% confidence interval is greater than 25%.

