16.5 Operation Characteristics

The probability of declaring that this regimen warrants further studies (i.e., statistical power) under various success proportions can be tabulated as a function of the true success proportion as shown in the following table.

If the true success proportion is:	25%	47%
then the probability of stopping early is:	0.4597	0.0037
and the probability of declaring that the regimen warrants further studies is:	0.0651	0.7923

The operation characteristics were calculated using simulation with 10,000 replications. PFS6 of 25% is generated using Weibul distribution (scale=0.3, shape=0.6667) PFS6 of 47% is generated using Weibul distribution (scale=0.73, shape=0.8850)

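### At the planned 2 patients per month with no accrual hold, the futility look comes after all, or all but one or two, of the 22 evaluable patients are enrolled, so the 0.4597 in section 16.5 is not a chance of limiting enrolment

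*Combined protocol and SAP*

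**What the plan says.** Section 16.3: "We plan to accrue 22 evaluable patients", with the calculation "assuming a 1-sided significance level of 0.1 and an accrual rate of 2 patients per month". The section does not say whether the rate counts evaluable or registered patients, or whether arrivals are constant or random. It adds two conditions on the look: "The interim analysis will be considered non-binding" and "The accrual will not be halted for the interim analysis". Projected maximum accrual is 25, of whom 3 allow for patients who turn out not to be evaluable.

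Section 16.4: "Interim analysis will be conducted around 6 months after the 11th evaluable patient has been enrolled", once available third-scan data have been entered. The consequence of a poor result is "The study may temporarily close to accrual if the PFS6 rate is" 30% or lower. No other action is described. Section 16.1 sets six months equal to 27 weeks.

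Section 16.5 has a row beginning "then the probability of stopping early is", with 0.4597 at a true PFS6 of 25% and 0.0037 at 47%. Section 1.6 calls the trial two-stage.

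**The concern.** A two-stage label and a 46% early-stopping probability under the null tell an ethics committee, monitoring board or funder that an ineffective regimen has nearly an even chance of being given to fewer patients. That holds only if patients remain to be enrolled when the look is made. Waiting about 6 months after the 11th patient while enrolment continues uses up the whole second stage at the planned rate. The stake is the accuracy of a stated patient-protection property. The final efficacy inference is not in question.

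**Working it through.** **Inputs.** 22 evaluable patients, 2 per month, no hold, non-binding look, 25 maximum (16.3). Look about 6 months after the 11th evaluable patient, boundary 30%, success if the lower 80% confidence limit exceeds 25% (16.4). Six months = 27 weeks = 27 × 7 / 30.44 = 6.21 months (16.1). Weibull models (16.5).

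**1. The final rule reproduces.** With complete follow-up, the 80% logit-Greenwood lower limit is 0.245 for 8/22 and 0.284 for 9/22, so success needs at least 9 of 22. Exact binomial: P(X ≥ 9 | 22, 0.25) = 0.075 and P(X ≥ 9 | 22, 0.47) = 0.783. Simulating the stated Weibull models at 27 weeks without stopping gives power of about 0.80. The plan states 80% and 0.7923.

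**2. Timeline at a constant rate r of evaluable patients.** The 11th enters at 11/r, the look is at 11/r + 6.0 to 6.21, and the 22nd enters at 22/r. Data-entry time is not included.

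| Reading of the 2 per month | r | 11th | Look | 22nd | Enrolled at look |
|---|---|---|---|---|---|
| Evaluable | 2.00 | 5.5 | 11.5–11.7 | 11.0 | 22 of 22 |
| Registered, 22/25 evaluable | 1.76 | 6.25 | 12.25–12.46 | 12.5 | 21 of 22 |
| FGF19 untested, 31/36 positive | 1.72 | 6.39 | 12.39–12.60 | 12.77 | 21 of 22 |
| Both losses | 1.52 | 7.26 | 13.26–13.47 | 14.51 | 20 of 22 |

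The 31/36 comes from section 1.4, where 5 of 36 screened patients showed no FGF19 expression. Applying it to the accrual rate is an assumption, and combining it with 22/25 may double count. The rule has someone left to stop only if 22/r > 11/r + look delay, that is r < 11/6.21 = 1.77 to 11/6.0 = 1.83 per month.

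**3. Random arrivals at 2 evaluable per month.** The gap from 11th to 22nd is Gamma with shape 11 and rate 2. P(gap ≤ 6.0 to 6.21 months) = 0.65 to 0.70, so there is a 30–35% chance that accrual is still open; mean enrolment at the look is 21.1–21.2. In 10,000 simulated trials per setting, with Kaplan-Meier PFS6 at 27 weeks:

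| | Null | Alternative |
|---|---|---|
| Boundary crossed with accrual open, constant arrivals | 0 | 0 |
| Boundary crossed with accrual open, Poisson arrivals | 0.22 | 0.03–0.04 |
| Mean evaluable patients saved, Poisson arrivals | 0.55–0.58 | 0.07–0.11 |

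**4. The stopping row does not follow from the 30% boundary.** With 11 complete patients, a rate of 30% or less means at most 3 of 11 (3/11 = 27.3%, 4/11 = 36.4%). P(X ≤ 3 | 11) is 0.713 at 25% and 0.157 at 47%. Simulation gives 0.74–0.75 and 0.15 using the first 11 patients, and 0.73 and 0.08–0.09 using everyone enrolled. A cutoff of at most 2 of 11 gives 0.455 at 25%, near the stated 0.4597, but 0.050 at 47%, not 0.0037. Even with 22 completely followed patients, a count cutoff that stops with probability 0.4597 under the null stops with probability of at least 0.008 to 0.014 under the alternative.

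**The case against.** The strongest reply is that nothing is hidden. Section 16.3 openly says that accrual continues and that the look is non-binding, and section 16.4 says only that the study may close temporarily. The final rule, sample size and power stand without the look. All of this is correct, but none of it tells the reader that the stopping row has almost no bearing on enrolment. A non-binding rule weakens the implied protection further.

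Second, the margin is only 0.5 to 0.7 month and depends on how the rate is read. A reader might infer that the design can never stop early. The documents do not support that: at about 1.8 evaluable patients per month or fewer the rule can act, and random arrivals sometimes leave room even at 2. Amendment 4 was made to improve recruitment (section 1.4), so slower accrual is plausible; no enrolment dates are given, so the actual rate is unknown. This part of the objection stands and limits the point to the planning assumptions.

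Third, a reader might infer that the table promises to spare 11 patients. Section 16.5 gives a probability and no patient count, so that comparison is not available. A reader might also conclude that the trial is simply single-stage. It is not, because section 16.4 keeps an interim look with a possible closure.

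Finally, crossing the boundary could still bring a futility conclusion before the final analysis near month 17 (11.0 + 6.2). That is possible, but the documents describe no such action.

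**Conclusion.** The point holds for the plan's own assumptions. At 2 patients per month without a hold, 22 of 22 evaluable patients are enrolled at the look, or 20 to 21 if the rate counts registered or FGF19-untested patients. The chance of closing accrual while it is open is 0 with constant arrivals at 2 evaluable per month. With Poisson arrivals at that rate it is about 0.22 under the null, for a mean saving of about 0.6 patient. The figure of 0.4597 should not stand as an early-stopping property: it overstates what the look can do for enrolment, and it differs from the roughly 0.7 that the 30% boundary yields under the null.

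This rests on the look falling 6.0 to 6.21 months after the 11th evaluable patient. Data-entry time would move it later and so reduce any saving. The type I error and power of the final rule are not in doubt. The text should be corrected, but the trial's main conclusion does not depend on it.

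**What to change.** In section 16.5:

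- Replace the early-stopping row with the re-simulated probability of crossing the 30% boundary: about 0.7 at the null and 0.08 to 0.16 at the alternative, depending on which patients enter the interim estimate. State which patients those are.
- Give beside it the expected number enrolled at the look under the assumed rate and the no-hold rule, and say whether the rate counts evaluable or registered patients.
- State that the non-binding look is not expected to reduce enrolment at the planned rate, and acts only if accrual falls below about 1.8 evaluable patients per month.
- Give the operating characteristics of the final rule without stopping: at least 9 of 22, exact type I error 0.075, power 0.783.

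This costs a short re-simulation and a text amendment, with no change in conduct. The downside is a less favourable stated early-stopping property. Pausing accrual after the 11th evaluable patient would give the look something to act on, but it would lengthen the trial; it is a trade-off for the sponsor and not required. A pause would not rescue the present row, because its figures would still need to be re-derived.

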16.4 Statistical Analysis

Interim analysis will be conducted around 6 months after the 11th evaluable patient has been enrolled and the data from the third re-staging scan, if available, has been entered into the electronic database. The PFS6 rate will be calculated using the Kaplan-Meir method. The study may temporarily close to accrual if the PFS6 rate is $\leq 30\%$ at the interim analysis.

Final analysis will be conducted around 6 months after the 22nd evaluable patient has been enrolled and the data from the third re-staging scan, if available, has been entered into the electronic database. The PFS6 rate will be calculated using the Kaplan-Meir method and 80% confidence interval will be calculated using Greenwood's formula with logit transformation. The combination therapy will be declared as promising for future study if the lower bound of the 80% confidence interval is greater than 25%.

16.5 Operation Characteristics

The probability of declaring that this regimen warrants further studies (i.e., statistical power) under various success proportions can be tabulated as a function of the true success proportion as shown in the following table.

If the true success proportion is:	25%	47%
then the probability of stopping early is:	0.4597	0.0037
and the probability of declaring that the regimen warrants further studies is:	0.0651	0.7923

The operation characteristics were calculated using simulation with 10,000 replications. PFS6 of 25% is generated using Weibul distribution (scale=0.3, shape=0.6667) PFS6 of 47% is generated using Weibul distribution (scale=0.73, shape=0.8850)

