11.1 Schedule of Evaluations

For the purposes of this study, patients should be reevaluated every 9 weeks. In addition to a baseline scan, confirmatory scans should also be obtained 4-6 weeks following initial documentation of objective response.

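### The stopping-early probabilities in Section 16.5 (0.4597 at 25%, 0.0037 at 47%) do not follow from the interim rule in Section 16.4, which is met in about 68-75% and 7-16% of trials

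*Combined protocol and SAP*

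**What the plan says.** - **Section 16.4, timing:** "Interim analysis will be conducted around 6 months after the 11th evaluable patient has been enrolled", once third re-staging data, if available, are in the database.
- **Section 16.4, rule:** "The study may temporarily close to accrual if the PFS6 rate is" 30% or lower, by Kaplan-Meier. The regimen is promising at the end if the lower 80% confidence bound (Greenwood, logit) exceeds 25%.
- **Section 16.3:** one futility look. "The interim analysis will be considered non-binding", and accrual continues during it. The target is 22 evaluable patients at 2 per month.
- **Section 16.5:** the row "then the probability of stopping early is" shows 0.4597 at 25% and 0.0037 at 47%. The row below it, the probability that the regimen warrants further study, shows 0.0651 and 0.7923. "The operation characteristics were calculated using simulation with 10,000 replications". Weibull curves are given with scale 0.3, shape 0.6667 (null) and scale 0.73, shape 0.8850 (alternative). No time unit, interim cut-off or interim analysis set is given.
- **Section 16.1:** "Six months is defined as 27 weeks".
- **Section 11.1:** "For the purposes of this study, patients should be reevaluated every 9 weeks".

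**The concern.** With about 11 informative patients, a 30% cut-off lies only a little above the 25% null and not far below the 47% alternative. Such a rule should be met most of the time under the null and in a noticeable minority of trials under the alternative. The printed row shows neither: it is too low at 25% and close to zero at 47%.

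This row is the only information in the documents on how often the futility look would misfire. Because the look is advisory, its effect depends on how much weight people give the result. Anyone relying on 0.0037 would read a PFS6 at or below 30% as near-conclusive evidence against the regimen.

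**Working it through.** **1. Exact check on the first 11 patients.** With all 11 followed to the landmark, PFS6 ≤ 30% means X ≤ 3, because 3/11 = 27.3% and 4/11 = 36.4%. With X ~ Binomial(11, p):

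- p = 0.25: 0.0422 + 0.1549 + 0.2581 + 0.2581 = **0.713** (printed 0.4597)
- p = 0.47: 0.0009 + 0.0090 + 0.0401 + 0.1067 = **0.157** (printed 0.0037)

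**2. Simulation error.** With 10,000 replications the standard error is √[p(1−p)/10,000]: 0.0050 at 0.4597 and 0.0006 at 0.0037. The gaps are 0.713 − 0.4597 = 0.253 and 0.157 − 0.0037 = 0.153.

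**3. Kaplan-Meier simulation of the rule as written.** Settings: 100,000 replicates, 22 patients at 2 per month, cut-off ≤ 30%, progression dated continuously, Weibull time unit assumed to be years. Entries are P(line met) at null / alternative.

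| Curves and landmark | First 11 | All enrolled at the look |
|---|---|---|
| Printed Weibulls, 27 weeks | 0.749 / 0.143 | 0.720 / 0.083 |
| Printed Weibulls, 0.5 year | 0.724 / 0.129 | 0.693 / 0.073 |
| Rescaled to exactly 25% / 47% at 27 weeks | 0.713 / 0.157 | 0.683 / 0.094 |

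Overall this is 0.68-0.75 / 0.07-0.16. At the alternative the ratio to the printed value runs from 0.073/0.0037 ≈ 20 to 0.157/0.0037 ≈ 42.

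**4. Does the same model reproduce the other row?** With complete follow-up, the final rule requires at least 9/22: the logit lower bound is 0.245 at 8/22 and 0.284 at 9/22. P(X ≥ 9) is 0.075 at 25% and 0.783 at 47%. The simulated success row is 0.056-0.074 / 0.782-0.833 if the stop is ignored and 0.048-0.072 / 0.729-0.820 if it is obeyed. Together these ranges contain the printed 0.0651 / 0.7923. The inputs are therefore adequate, and only the stopping row disagrees.

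**5. Could another cut-off explain it?** Not a single one, with continuous dating:

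- First 11, ≤ 2/11: 0.455 / 0.050. The first value is close; the second is about 13.5 times the printed 0.0037.
- All enrolled, cut-off tuned to 0.46 at the null (0.223-0.235): alternative 0.024-0.034.
- All enrolled, cut-off tuned to 0.0037 at the alternative (0.126-0.145): null 0.13-0.18.

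**6. Could event dating explain it?**

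| Progression dated at scans | Stopping row | Success row |
|---|---|---|
| Exactly every 9 weeks, 27-week landmark | 0.67-0.75 / 0.09-0.16 | about 0.05-0.06 / 0.75-0.80 (printed curves) |
| Exactly every 9 weeks, 26-week landmark | 0.35-0.47 / 0.008-0.035 | 0.26-0.34 / 0.95-0.98 |
| Scans ±7 days, 27-week landmark | 0.57-0.70 / 0.06-0.09 | 0.13-0.19 / 0.87-0.93 |

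The 26-week landmark comes nearest to the stopping row. It conflicts with Section 16.1 and moves the success row far from its printed values. In that variant, too, no single cut-off on all enrolled matches both figures: a null value near 0.46 goes with 0.012-0.019 at the alternative, and 0.0037 at the alternative goes with 0.23-0.30 at the null.

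**The case against.** **The range could be wider.** Section 16.4 says only about 6 months, and it also waits for data entry. A look 3 to 6 months late, using everyone enrolled, gives about 0.70-0.72 / 0.034-0.046. A second run with symmetric ±7-day scan windows gave 0.51-0.61 / 0.03-0.08. Both are fair sensitivity checks, but neither rescues the row. Even 0.034 is about 9 times 0.0037. A 3-to-6-month delay stretches the stated timing, and a 1-to-2-month delay still gives 0.69-0.75 / 0.06-0.16. The scan-window variants also move the success row well away from 0.0651 / 0.7923, so they cannot be the model behind the table.

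**Stopping is undefined.** The study only may close, temporarily, and the look is non-binding, so the row might count something other than the line being met. That is possible, but the documents define no other event. If another was meant, the table needs to say so.

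**The harm is small.** At 2 per month patient 11 enters at month 5 and patient 22 at month 10.5, while the look falls at about month 5 + 6.2 = 11.2. On the planned rate there is almost no accrual left to close. This stands, though Section 1.4 describes 11 patients with FGF19 expression enrolled against a target of 22 and a need to improve recruitment. With slower accrual the look would come before accrual ends and would rest mostly on the first 11 patients, where the false-signal rate is highest.

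**Conclusion.** The concern holds. Under the rule in Section 16.4, the futility line is met in about 68-75% of trials at a true PFS6 of 25% and 7-16% at 47%, against the printed 46% and 0.4%. These ranges assume a look at about 6 months, 2 patients per month and continuous event dating; exact 9-week scans at 27 weeks give nearly the same (67-75% and 9-16%). The simulations also assume Weibull time in years. The binomial figures (0.713 / 0.157) need no Weibull assumption.

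The simulation code is not in the documents, so the cause (threshold, analysis set, timing or event dating) cannot be identified. The printed power and type I error are not shown to be wrong, and the final decision rule is unaffected. The consequence is limited to the weight given to the interim result. The documents do not say whether the look has taken place. This should be fixed, but it does not threaten the design.

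**What to change.** 1. State in Section 16.5 the cut-off, interim analysis set, landmark, event dating and Weibull time unit that were simulated, and whether the stop was applied when computing the row on warranting further study.
2. Then do one of two things. Either rerun the table for the 16.4 rule as written and replace the row; on exact 25% / 47% curves with continuous dating and no delay, expect about 0.71 / 0.16 on the first 11 or 0.68 / 0.09 on all enrolled. Or, if a different rule was intended, correct Section 16.4 so that it reproduces the row.
3. In the rerun, use Weibull scales that give 25% and 47% at 27 weeks. If the unit is years, t = 27 × 7/365.25 = 0.517, and t/(−ln S)^(1/shape) gives scales of about 0.317 and 0.711. The printed scales give about 23.7% and 47.8% there. This is a tidying point and does not explain the row.

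The cost is one rerun of the existing R simulation and a few sentences. The reported chance of a false futility signal will look less favourable. Sample size and the final decision rule do not change.

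### The operating-characteristics table in 16.5 does not describe the design written in 16.1 to 16.4: its Weibull inputs miss their 25% and 47% labels, power at a true 47% is at most 78%, and its early-stopping row does not follow from the 30% rule.

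*Combined protocol and SAP*

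**What the plan says.** Section 16.1 makes the primary endpoint PFS at 6 months and fixes the time: "Six months is defined as 27 weeks".

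Section 16.3 states "With 22 evaluable patients, we have 80% power to detect PFS6 from 25% (historical control) to 47" per cent, "assuming a 1-sided significance level of 0.1 and an accrual rate of 2 patients per month". It adds that "The interim analysis will be considered non-binding" and that accrual continues during it.

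Section 16.4 places the interim about 6 months after the 11th evaluable patient. The study may close temporarily if the Kaplan-Meier PFS6 is 30% or lower. At the end, the regimen is called promising if the lower limit of an 80% confidence interval (Greenwood, logit scale) exceeds 25%.

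Section 16.5 tabulates results from 10,000 simulated trials. In the 25% column, early stopping is 0.4597 and declaring success 0.0651. In the 47% column they are 0.0037 and 0.7923. The inputs are given as "PFS6 of 25% is generated using Weibul distribution (scale=0.3, shape=0.6667") and "PFS6 of 47% is generated using Weibul distribution (scale=0.73, shape=0.8850"). No time unit is stated.

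**The concern.** The table is the only support in the plan for the 80% power claim, and the only information on how often the futility look would stop the trial. Two things can be checked directly: whether the Weibull parameters give the proportions in the column headings, and whether the tabulated probabilities follow from the rules in 16.4. If either fails, anyone using the table to judge the risk of missing a useful regimen, or of stopping one early, is reading figures for a different design.

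**Working it through.** **Inputs.** n = 22; null 25%, alternative 47%; one-sided 0.1; 2 patients per month (16.3). Six months = 27 weeks (16.1). Interim after the 11th patient, threshold 30%; final lower limit above 25% (16.4). Weibull (scale, shape) = (0.3, 0.6667) and (0.73, 0.8850) (16.5).

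**1. Decision rule in counts.** With all 22 followed to the PFS6 time and no drop-out, Kaplan-Meier equals x/22 and the limit is logit(p) − 1.2816 × √(1/(22p(1−p))), back-transformed.
- x = 8: p = 0.3636; −0.5596 − 1.2816 × 0.4432 = −1.1276, so 24.5%. Fails.
- x = 9: p = 0.4091; −0.3677 − 1.2816 × 0.4336 = −0.9234, so 28.4%. Passes.

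Success therefore means at least 9 of 22.

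**2. The plan's own power figure.** P(X ≥ 9 | 22, 0.47) = 0.783. This is close to 80% but below it. It is also the ceiling under these assumptions, because a futility stop can only lower power. The printed 0.7923 is 0.0091 higher. The Monte Carlo standard error at 10,000 runs is √(0.7923 × 0.2077/10,000) = 0.0041, so the gap is about 2.2 standard errors.

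**3. Weibull inputs.** S(t) = exp(−(t/scale)^shape). If the scale were in months, both values at 6 months would be below 0.2%, so years is the workable unit.

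| Time | Labelled 25% | Labelled 47% |
|---|---|---|
| 0.5 year | 24.5% | 48.9% |
| 27 weeks (0.517 to 0.519 year) | 23.7% | 47.7 to 47.8% |

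The first curve reaches 25% at 0.490 year and the second reaches 47% at 0.531 year, so no common time gives both. At either reading the null lies below its label and the alternative above it.

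**4. Operating characteristics at exactly 25% and 47%.** Three of 11 is 27.3%, so the 30% rule on the first 11 stops at 3 or fewer. At 2 patients per month, patient 11 enters at 11/2 = 5.5 months, the interim falls at about 5.5 + 6 = 11.5 months, and patient 22 enters at 22/2 = 11 months. All 22 would then be enrolled at the interim, many with incomplete follow-up, and Kaplan-Meier on all of them has to be simulated.

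| Handling of the interim | Stop, 25% | Stop, 47% | Success, 25% | Success, 47% |
|---|---|---|---|---|
| Not enforced (exact) | – | – | 0.075 | 0.783 |
| Enforced, KM on all enrolled (simulated) | about 0.68 | about 0.09 | about 0.07 | about 0.77 |
| Enforced, first 11 only (exact) | 0.713 | 0.157 | 0.064 | 0.729 |
| **Printed in 16.5** | **0.4597** | **0.0037** | **0.0651** | **0.7923** |

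Neither enforced version gives the printed stopping row. A cut at 2 or fewer of 11 gives 0.455 at 25%, near 0.4597, but 0.050 at 47%, far from 0.0037. It is also not the written rule.

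**The case against.** The best defence is that little is at stake. The interim is non-binding and 16.4 says only that the study may close temporarily, so the relevant power is 0.783, under 2 points from a rounded 80%. At 27 weeks the alternative is less than 1 point from its label. No threshold, sample size or analysis changes. All of that stands, and it limits the size of the point. It does not explain the table, which reports early stopping beside power and so invites the reading that the stop was applied.

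Four stronger readings are tempting and are not supported.

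- **That true power is 73%.** This needs a stop that is always obeyed, on exactly the first 11 patients. The plan describes neither. At the stated accrual with Kaplan-Meier on all enrolled, the enforced figure is about 0.77. Slower accrual would bring the interim set closer to the first 11.
- **That the table was simulated at 24.5% or 47.8%.** With a stop at 2 or fewer of 11, the null figure 0.0651 is matched at 0.5 year, but power there is 0.824. At 27 weeks power is about 0.794 to 0.796, but the type I error is about 0.053 to 0.054. Each column fits only at a different time, and the stopping probability of about 0.045 at 27 weeks is roughly twelve times the printed 0.0037. How the table was produced cannot be inferred.
- **That type I error is not controlled.** At a true 25% it is 0.064 to 0.075 in the three versions above, below 0.10.
- **That the sample size is inadequate.** A shortfall of about 2 points with the interim not enforced does not show that.

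**Conclusion.** The point holds as an error in stated figures. The Weibull parameters do not give 25% and 47% at any common time. Power at a true 47% is 0.783 with the interim not enforced, about 0.77 or 0.73 with it enforced on all enrolled or on the first 11, and so below both 80% and 0.7923. The shortfall is small unless futility is enforced. The clearest mismatch is the early-stopping row: the 30% rule gives about 0.68 to 0.71 at 25% against 0.4597, and 0.09 to 0.16 at 47% against 0.0037.

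This rests on the scale being in years, no drop-out before 27 weeks, and accrual at 2 evaluable patients per month. The conclusion on the Weibull labels depends only on the first of these.

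**What to change.** Rerun the simulation with parameters that give exactly 25% and 47% at 27 weeks. Keeping the printed shapes and 27/52 = 0.5192 year, scale = 0.5192/(−ln p)^(1/shape). This gives 0.5192/1.632 = 0.318 for the null and 0.5192/0.728 = 0.713 for the alternative. Apply the 30% interim rule as written.

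In 16.5, state the time unit, the evaluation time, which patients enter the interim estimate and whether the stop is enforced, and replace both rows of the table. In 16.3, restate power as about 78% with the interim not enforced, and add the simulated lower figure if it is enforced.

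The cost is one rerun of an existing simulation and a slightly less favourable power statement. Sample size and decision rule stay as they are.
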